4.4 Concomitant Medications/Treatments

4.4.1 Required concomitant medications

- 4.4.1.1 Tylenol (acetaminophen) 650 mg PI 30 minutes prior to each infusion or equivalent as per standard practice.
- 4.4.1.2 Benadryl (diphenhydramine) 50 mg IVPB 30 minutes prior to each infusion or equivalent as per standard practice.

4.4.2 Allowed concomitant medications

- 4.4.2.1 Solumedrol 125 mg IV over 15 minutes as needed for infusion reactions.
- 4.4.2.2 Symptomatic treatment as needed for nausea, vomiting, and/or diarrhea, including 5-HT3 antagonists, corticosteroids, benzodiazepines, and anti-motility agents.
- 4.4.2.3 Topical and systemic treatment for rash, including corticosteroids.
- 4.4.2.4 Hormonal birth control medications.
- 4.4.2.5 Concurrent antiviral therapy for HBV surface antigen positivity.
- 4.4.2.6 G-CSF (Filgrastim), including Neulasta®, may be added for low ANC while any requisite dose reduction in study agent is instituted, at treating physician's discretion.

4.4.3 Concomitant medications and treatments NOT allowed

- 4.4.3.1 Concurrent chemotherapy, radiotherapy within 28 days prior to registration, or other investigational agents within 14 days prior to registration.

4.5 Other Modalities or Procedures

No other treatment modalities or procedures are required as part of the study treatment. Any patient receiving radiation therapy and/or surgery related to progression of malignancy will be removed from protocol therapy. In addition, any patient that subsequently undergoes stem cell transplant will be removed from protocol therapy.

4.6 Duration of Therapy

In the absence of treatment delays due to adverse events, treatment may continue for one year or until:

- 4.6.1 Disease progression
- 4.6.2 Inter-current illness that prevents further administration of treatment
- 4.6.3 Unacceptable adverse event(s)
- 4.6.4 Patient decides to withdraw from the study, OR
- 4.6.5 General or specific changes in the patient's condition render the patient unacceptable for further treatment in the judgment of the investigator.

Please also refer to Section 4.8 for additional information regarding off-treatment and off-study criteria.

4.7 Duration of Follow Up

Once patients are off treatment (whether treatment is completed or they are withdrawn for any reason) patients will be followed with at least one clinic visit every three months, for up to one year from discontinuation of treatment, then every six months up to 3 years from discontinuation of treatment, or until death, whichever occurs first. Patients removed from treatment for unacceptable adverse events will be followed until resolution or stabilization of the adverse event.

4.8 Removal of Subjects from Treatment and/or Study

Patients can be removed from the study treatment and/or study at any time at their own request, or they may be withdrawn at the discretion of the investigator for safety, behavioral, or administrative reasons. The reason(s) for discontinuation must be documented and may include:

- 5.5.1 Patient voluntarily withdraws from treatment (follow-up permitted);
- 5.5.2 Patient withdraws consent (termination of treatment and follow-up);
- 5.5.3 Patient is unable to comply with protocol requirements;
- 5.5.4 Patient demonstrates disease progression (unless continued treatment with study drug is deemed appropriate at the discretion of the investigator);
- 5.5.5 Patient experiences toxicity that makes continuation in the protocol unsafe;
- 5.5.6 Treating physician judges continuation on the study would not be in the patient's best interest;
- 5.5.7 Patient becomes pregnant (pregnancy to be reported along same timelines as a serious adverse event);
- 5.5.8 Development of second malignancy (except for basal cell carcinoma or squamous cell carcinoma of the skin) that requires treatment, which would interfere with this study;
- 5.5.9 Patient is lost to follow-up. If a research subject cannot be located to document survival during the follow-up period (up to 3 year after starting study treatment), the subject may be considered "lost to follow-up." All attempts to contact the subject during the follow-up period must be documented and approved by the Data Monitoring Committee.

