NCI	National Cancer Institute
NHL	Non-Hodgkin Lymphoma
ORR	Overall Response Rate
OS	Overall Survival
PBMCs	Peripheral Blood Mononuclear Cells
PD	Progressive Disease
PFS	Progression Free Survival
p.o.	per os/by mouth/orally
PR	Partial Response
PRR	Partial Response Rate
RP2D	Recommended phase II dose
QOD	Every other day
SAE	Serious Adverse Event
SD	Stable Disease
SGOT	Serum Glutamic Oxaloacetic Transaminase
SPGT	Serum Glutamic Pyruvic Transaminase
WBC	White Blood Cells

STUDY SCHEMA

- DLT period (Phase I only): 21 days of induction
- Duration of treatment (Phase I and II): one year, or until POD (whichever occurs first)
- Primary objective assessment: toxicity after week 4 treatment (Phase I only); scans after induction treatment and/or after consolidation treatment (if applicable) (Phase II only)

*This may be repeated once at discretion of treating investigator; see Section 4.0 (TREATMENT PLAN) for details.

DOSING SCHEMA (in weeks, continued for one year total, or until POD)

STUDY SUMMARY

Title	A Phase I-II Trial of Brentuximab Vedotin Plus Rituximab as Frontline Therapy for Patients with Lymphomas of Immunosuppressed States
Version Date	June 14, 2017 (Amendment 8)
Protocol Number	NU 12H09
Phase	I/II
Methodology	Open-label, single-arm
Study Duration	Approximately 30 months
Study Center(s)	Northwestern University, University of Chicago
Objectives	
Primary objectives: Phase I: Evaluate the safety of brentuximab vedotin and rituximab in patients with immunosuppressed lymphoid malignancies and to determine the recommended phase II dose (RP2D) of the combination. Phase II: Evaluate the efficacy of brentuximab vedotin and rituximab in patients with immunosuppressed lymphoid malignancies.
 
Secondary objectives: Phase II:
 
 1. Further evaluate the frequency and severity of toxicity. 2. Further evaluate the efficacy as measured by one-year PFS and OS. 3. Determine the effects of the combination of brentuximab vedotin and rituximab on markers of EBV activation and proliferation. 4. Further evaluate efficacy as measured by time to initiation of cytotoxic chemotherapy. 5. Further evaluate efficacy as measured by observed rates of graft rejection. 
Exploratory objectives (Phase I and II): Correlate response and outcomes with CD30 expression and EBV markers and levels.

Number of Subjects	Phase I: 3-9 patients; Phase II: 24 patients

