Based upon this hypothesis, we propose to conduct a Phase I/II trial combining Brentuximab vedotin with rituximab in patients with newly-diagnosed lymphoid malignancies that are CD30+ and/or EBV+ (as defined by evidence of EBV in either the tumor biopsy specimen, or by positive EBV viral load at time of diagnosis). Phase I will aim to establish the RP2D (which will be defined as the MTD; it is expected that the combination dose of each agent will be identical to that when each is used alone). Phase II will aim to evaluate the efficacy of this regimen as measured by response rates. As we expect the majority of patients to have a history of significant immunosuppression (based upon observed patterns in our patient population), we do not plan to stratify patients based upon transplant history status (ie, those with history of solid organ transplant, versus those without). However, exploratory analyses of this factor may eventually be considered.

In light of the potentially aggressive course of some cases of PTLD and other EBV-related malignancies, we propose a weekly dosing of each agent before transitioning to a treatment schedule of every 3 weeks. Of note, the safety and efficacy of weekly induction has been shown for both brentuximab vedotin and rituximab when used as single agents [21, 39].

It would perhaps be reasonable to have concerns about offering the treatment proposed in this study as frontline therapy to eligible young, otherwise-healthy patients who could also be candidates for other accepted, well-established, frontline therapies with outcomes that are reasonably well-described. However, it is our contention that the TRM associated with early aggressive therapy, makes alternative treatments, such as that offered in this trial, a very attractive means of attempting to reduce risk of early TRM, and that this alone warrants its evaluation as a front-line regimen. Moreover, this trial specifically recommends early cessation of treatment protocol, in favor of more aggressive chemotherapy, for those patients who fail to achieve adequate response, per the discretion of the treating investigator. We believe that this introduces a safety mechanism necessary to the treatment of this patient population that will have a variety of potential clinical acuity.

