4.1.1.1 Brentuximab vedotin

Induction: 1.2 mg/kg IV infusion over 30 minutes, weekly x 3 (1 cycle = 4 weeks; no brentuximab vedotin is given during the fourth week)

Consolidation (optional): Identical to Induction. Those patients who achieve response (PR or CR) after the Induction course may receive an additional treatment of the same (termed Consolidation). In addition, any patients achieving CR to induction, in whom avoidance of Maintenance therapy is sought, can receive consolidation as their final planned therapy. See section 4.1.3 for stipulations regarding stable disease.

Maintenance: 1.8 mg/kg IV infusion over 30 minutes once every 3 weeks (1 cycle = 3 weeks), for a total of one year from the first induction dose or until progression of disease.

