4.1.1.2 Rituximab

Induction: 375 mg/m² IV infusion per standard protocol, once weekly for 4 weeks (1 cycle = 4 weeks)

Consolidation (optional): Identical to Induction. Those patients who achieve response (PR or CR) after the Induction course may receive an additional treatment of the same (termed Consolidation). In addition, any patients achieving CR to induction, in whom avoidance of Maintenance therapy is sought, can receive consolidation as their final planned therapy. See section 4.1.3 for stipulations regarding stable disease.

Maintenance: 375 mg/m² IV infusion per standard protocol, once every 6 weeks for a total of one year from the first induction dose or until progression of disease.

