Clinical suspicion of progressive disease (PD) or loss of response should be investigated radiographically, and if confirmed, will result in removal from active therapy (though any such patient will remain in study follow up; see 4.5, Duration of Therapy). In this case, it is strongly recommended that investigators consider early initiation R-CHOP or similar chemoimmunotherapy (off trial).

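### Section 4.8 item 5.5.4 lets study drug continue after progression without criteria, contradicting the mandatory stop at confirmed progression in section 4.1.5

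*Combined protocol and SAP*

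**What the plan says.** Three parts of the protocol govern what happens to study treatment at progression.

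- **Section 4.8, item 5.5.4** lists as a possible reason for discontinuation "Patient demonstrates disease progression", followed by the parenthesis "unless continued treatment with study drug is deemed appropriate at the discretion of the investigator". It gives no criteria, no time limit and no rule for reassessment.
- **Section 4.1.5** requires suspected progression or loss of response to be investigated radiographically and, "if confirmed, will result in removal from active therapy". The patient stays in follow-up, and early chemoimmunotherapy off trial is strongly recommended.
- **Section 4.1.3** says that patients with progressive disease at first re-staging should come off treatment and receive chemotherapy. Patients with stable disease should do the same, but the investigator may give them one Consolidation course. If they are then still stable or have progressed, they should come off.

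The general duration statements agree with 4.1.5. The Study Schema gives "one year, or until POD (whichever occurs first", and the maintenance text in 4.1.1.1 gives "for a total of one year from the first induction dose or until progression of disease". Section 4.1.1.2 and Table 2 say the same in substance. Section 4.6 also lists progression as an end of treatment, but refers the reader to 4.8 for further off-treatment criteria.

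**The concern.** Two operative sections give different instructions for the same event. A site that always stops at progression satisfies both. A site that uses the exception for a patient with confirmed progression follows 4.8 and breaches 4.1.5. Section 11.6 requires the study to be run as the approved protocol describes, so it is unclear whether that site has deviated.

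Two things could be at stake.

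- **Patient management.** Section 1.3 defends frontline use partly on the ground that "this trial specifically recommends early cessation of treatment protocol, in favor of more aggressive chemotherapy, for those patients who fail to achieve adequate response", and adds: "We believe that this introduces a safety mechanism necessary to the treatment of this patient population". Section 4.1.5 makes the stop firm once progression is confirmed. Item 5.5.4 loosens it again.
- **Time to first cytotoxic chemotherapy** (secondary; 2.4.5 and 6.2.5). The event is the first dose of cytotoxic chemotherapy, and progression does not count. Study drug given after progression could therefore lengthen this time in a patient whose disease is no longer controlled.

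**Working it through.** The plan gives no figure on this point, so the check sets the texts side by side.

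**Step 1. Do the two rules cover the same event?** Item 5.5.4 applies when a patient demonstrates progression. It is not limited to suspected progression. Section 4.1.5 applies once progression is confirmed. Confirmed progression therefore falls under both.

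**Step 2. Is the exception needed for unconfirmed progression?** No. Section 4.1.5 requires removal only after confirmation, so a patient with merely suspected progression can continue without it. Its only additional effect is on confirmed cases, where it conflicts.

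**Step 3. Which other texts bear on the conflict, and how strongly?**

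| Place | What it says at progression | Weight against item 5.5.4 |
|---|---|---|
| 4.1.5 | Confirmed progression leads to removal, stated with *will* | Categorical; direct contradiction |
| 4.1.3 | Progressive disease *should* come off; bounded continuation for stable disease only | Does not fit the exception, but not absolute |
| Schema, 4.1.1.1, 4.1.1.2, Table 2 | One year or until progression | Consistent with 4.1.5, but one phrase repeated |
| 4.6.1 | Progression ends treatment | Not independent, because 4.6 points to 4.8 |

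By section, seven places end treatment at progression. Setting aside the four that repeat the duration phrase and the one that defers to 4.8 leaves 7 − 4 − 1 = 2, namely 4.1.5 and 4.1.3. Only 4.1.5 is categorical.

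**Step 4. Is the exception coherent with 4.1.3?** Continuation in stable disease is capped at one Consolidation course, with removal if there is still no response. Continuation in progressive disease, the worse outcome, would have no cap, criteria or reassessment under item 5.5.4. In 4.1.3 the investigator's discretion for progressive disease concerns the chemotherapy that follows, not further study drug.

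**Step 5. Which endpoints could move?**

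- *Time to first cytotoxic chemotherapy:* it could lengthen. The documents give no progression rate and no number treated past progression, so no size can be computed.
- *PFS:* it is dated to progression (or death, 2.4.2), so later study drug does not move the date.
- *Primary response endpoint:* no effect is shown. Section 4.1.3 and Table 1 offer Consolidation after complete or partial response, or stable disease, not after progression.

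**The case against.** The strongest defence is that 4.8 is a documentation list rather than a dosing rule. Its lead-in asks that reasons for discontinuation be recorded and says what they may include. The leftover 5.5.x numbering, and the amendment log's note that this language was moved into 4.8 to fit a template, suggest carried-over wording. On that view sites would follow the disease-specific rules in 4.1.3 and 4.1.5. This explains how the mismatch could have arisen but does not remove it: the parenthesis does more than name a reason, since it expressly contemplates further dosing.

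A second defence is the chain of references. Section 4.6 points to 4.8, and 4.1.5 itself points to the Duration of Therapy section. The first pointer stands, so 4.6.1 should not be counted as a separate contradiction. The pointer in 4.1.5 is attached to the remark that removed patients remain in follow-up. It does not qualify the removal.

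Three stronger readings are tempting, and the documents do not support them.

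- **A reader might count seven places against one.** Most of that count is repetition of a duration phrase, and a general duration with an exception stated elsewhere is ordinary drafting.
- **A reader might infer that item 5.5.4 dismantles a mandatory safety mechanism.** The mechanism in 1.3 is a recommendation and is itself left to the treating investigator, who can stop study drug and start chemotherapy at any time. Section 1.3 gives only limited support.
- **A reader might infer that a progressing patient could be carried into Consolidation and scored again for the primary endpoint.** No text provides Consolidation after progression.

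It is also fair to say that time to chemotherapy is a secondary endpoint in a single-arm trial and that section 10 attaches no hypothesis or threshold to it.

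**Conclusion.** The treatment-stopping rule is wrong as written, at the lowest severity. Item 5.5.4 permits, without criteria, what 4.1.5 rules out for confirmed progression, and it does not fit the bounded discretion in 4.1.3. Confidence in the textual contradiction is high, because it rests only on current text.

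The consequence is unquantified. An effect on time to first cytotoxic chemotherapy requires that at least one patient was treated past progression and that chemotherapy was delayed as a result. The documents give no evidence of either, so the effect may be zero. Sample size, alpha and power are untouched.

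**What to change.** Delete the parenthesis in item 5.5.4 so that 4.8 matches 4.1.5. No substitute wording is needed for suspected progression. If any patient received study drug after confirmed progression, report the number alongside time to first cytotoxic chemotherapy.

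The cost is one deletion and, if applicable, one reporting line. The downside is that investigators lose the discretion to continue study drug after confirmed progression, which 4.1.5 already withholds. If the sponsor does want that discretion, the alternative is to state it with conditions in 4.1.3, 4.1.5, 4.6 and the schema, and to say how such patients are counted for response. Deletion is simpler and fits the rest of the treatment plan. Neither route fully standardizes time to chemotherapy, because its timing after progression remains the investigator's decision under 4.1.3 and 4.1.5.

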4.9 Patient Replacement

During Phase I, all three patients enrolled at the starting dose level must be observed for one cycle (21 days), at which point the study will be temporarily suspended for toxicity evaluation, before which it may either be reopened for an additional cohort (at either the same dose or a lower dose), or proceed to Phase II (as outlined in sections 4.1.2 and 4.1.3). Any DLT noted at any point after treatment begins (up till the end of the DLT evaluation period) shall count toward the total number of DLT, and patients are not replaced. An exception will be made for those patients who are enrolled but, for whatever reason, never receive treatment; such patients should be replaced. If a patient is withdrawn from the study within 21 days of starting therapy, for whatever reason, but without experiencing a DLT prior to withdrawal, an additional patient may be added to that dose level. Patients missing more than three weeks' worth of doses due to toxicity will not be replaced since these patients will be considered to have experienced a dose limiting toxicity.

During Phase II, any patient who is enrolled but not treated on the study, or who completes fewer than two total cycles of therapy and is withdrawn for any reason except POD or toxicity, shall be replaced.

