2.3 Primary Endpoints

- 2.3.1 The primary endpoint for phase I, dose-limiting toxicity (DLT) will be defined as the occurrence of toxicity as detailed in section 4.2 (using CTCAE v 4.03), experienced during the first 3 weeks of study treatment. The MTD, which constitutes the RP2D, will be defined as described in Section 11 (Study Design).
- 2.3.2 The primary endpoint for phase II, response after induction or induction/consolidation, will be defined as the detection of SD, PR, or CR by CT or PET/CT, and/or resolution of marrow-only involvement. CR and PR will each be assessed according to the Revised Response Criteria for Malignant Lymphoma. Assessments will be performed after induction and/or consolidation treatment (if applicable).

2.4 Secondary Endpoints:

- 2.4.1 Adverse events will be defined as those included in CTCAE v 4.03. The occurrence and severity of each will be recorded.
- 2.4.2 PFS will be defined as the time elapsed between treatment initiation and tumor progression or death from any cause (whichever occurs first), with censoring of patients who are lost to follow-up. OS will be defined as freedom from death by any cause.
- 2.4.3 Best response will be assessed by CT or PET/CT according to the Revised Response Criteria for Malignant Lymphoma after induction and/or consolidation (if applicable) and every 12 weeks during maintenance treatment.
- 2.4.4 EBV activation and proliferation will be measured by viral loads as measured at time of enrollment and monthly thereafter in all enrolled patients, until completion of study therapy.
- 2.4.5 Time to initiation of cytotoxic chemotherapy will be defined as the time elapsed between treatment initiation, and time of first non-targeted cytotoxic chemotherapy.
- 2.4.6 Graft rejection will be defined as any of the following: documentation of new or progressive rejection by tissue biopsy of the graft; re-transplantation due to graft rejection; clinical diagnosis of new or progressive graft rejection, since start of treatment on protocol, as given by the patient's transplant physician. Escalation of intensity of immunosuppression will not, by itself, be considered evidence of graft rejection. (Note: patients with clinically active graft rejection will not be excluded from trial enrollment, but will not be considered to have treatment-emergent graft rejection unless progression of rejection is documented.)

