Patients achieving **PD** at first re-staging should be taken off treatment and treated with R-CHOP or similar chemotherapy at the discretion of the local treating investigator.

Patients achieving **SD** should likewise be taken off treatment and treated as above. However, at the discretion of the treating investigator, such patients may receive an additional treatment of the same termed "**Consolidation**".

Consolidation treatment is identical to Induction. If, after Consolidation treatment, these patients achieve CR or PR, they should proceed to Maintenance (see below for description). If, however, these patients are still SD or have progressed to PD, they should be taken off treatment and treated with R-CHOP or similar chemotherapy at the discretion of the local treating investigator.

Patients achieving **CR** or **PR** after the Induction course may receive an additional treatment of the same termed "**Consolidation**". Consolidation treatment is identical to Induction. For patients achieving CR after Induction, in whom avoidance of maintenance therapy is sought, Consolidation may be given as their final planned therapy. Patients who achieve CR after Induction may proceed directly to Maintenance therapy at the discretion of the treating investigator (for instance, if they are not likely to tolerate Consolidation therapy given the toxicity they experienced during Induction).

Following Consolidation, patients will proceed to **Maintenance:** 1.8 mg/kg IV infusion over 30 minutes once every 3 weeks (1 cycle = 3 weeks), for one year from starting induction or until progression of disease. At the discretion of the treating investigator, patients may discontinue brentuximab vedotin after 10 maintenance doses.

4.1.4 **Dose escalation on a per-patient basis (for both Phase I and Phase II):**

For any patient treated with a brentuximab vedotin dose of 0.8 mg/kg for 2 or more 21-day cycles without DLT, subsequent doses can be increased to 1.2 mg/kg, **but only at the discretion of the treating investigator.** *NOTE: the*

basis for escalation, or lack thereof, should be clearly documented in the Treatment eCRF.

4.1.5 Recommended treatment off study in the event of progressive disease or loss of response:

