6.2 Efficacy Definitions

6.2.1 Response and progression will be evaluated in Phases I and II using 2007 Revised Response Criteria for Malignant Lymphoma (modified).

6.2.1.1 Evaluable for objective response.

Only those patients who have measurable disease (at least 1cm) present at baseline, have received *at least three doses of brentuximab vedotin*, and have had their disease re-evaluated will be considered evaluable for response. These patients will have their response classified according to the definitions stated below. (Note: Patients who exhibit objective disease progression prior to the end of cycle 1 will also be considered evaluable.)

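### Read literally, 4.9 replaces Phase II patients taken off for stable disease after Induction, and the plan does not say whether they still count in the response rate

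*Combined protocol and SAP*

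**What the plan says.** - **Length of Induction (4.1.1.1).** Induction is a single cycle: "1 cycle = 4 weeks; no brentuximab vedotin is given during the fourth week".
- **SD at first re-staging (4.1.3).** After directing patients with PD to R-CHOP or similar, the section says that SD patients "should likewise be taken off treatment and treated as above". It then allows an exception: "at the discretion of the treating investigator, such patients may receive an additional treatment of the same termed" Consolidation, which is a second cycle.
- **Intent (1.3).** The rationale presents this route as a safety feature: "this trial specifically recommends early cessation of treatment protocol, in favor of more aggressive chemotherapy, for those patients who fail to achieve adequate response".
- **Replacement (4.9).** In Phase II, a patient who is enrolled but never treated, "or who completes fewer than two total cycles of therapy and is withdrawn for any reason except POD or toxicity, shall be replaced".
- **Evaluability (6.2.1.1).** Patients with measurable disease at baseline who have had at least three brentuximab vedotin doses "and have had their disease re-evaluated will be considered evaluable for response".
- **Response.** 2.3.2 says that the Phase II primary endpoint "will be defined as the detection of SD, PR, or CR by CT or PET/CT". The stopping rule in 7.5 uses CR or PR, and 9.2.2 contrasts CR/PR with SD/PD.
- **Design (10.1.2, 10.2).** The null ORR is 50% and the alternative 70%, with alpha below 0.05. The trial stops at eight or fewer responses in the first 15 enrolled, and 24 patients are planned. No final success cut-off and no analysis set for the primary endpoint are given.

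**The concern.** An SD patient who follows the default path in 4.1.3 has completed one cycle and comes off for a reason that is neither progression nor toxicity. On its wording, 4.9 makes replacement of that patient mandatory. PD patients are expressly kept, and responders who continue reach a second cycle. Among patients taken off because of their scan, the rule therefore reaches only those with SD.

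It does not reach all of them. A patient with the same scan who is given Consolidation completes two cycles and is not replaced. Whether a non-responder is replaced thus depends on an open-label decision made after the result is known.

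The primary analysis compares one arm with a fixed 50%. If a replaced patient also leaves the denominator, the ORR rises with no drug effect, and no control arm offsets it. The plan does not settle whether that happens.

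**Working it through.** **1. The plan's own figure.** A search for the optimal two-stage design with p0=0.50, p1=0.70, alpha below 0.05 and beta below 0.20 gives: stop at 8 or fewer of 15, succeed above 26 of 43. Its expected size under the null is 23.5, its alpha 0.0499 and its power 0.804. This reproduces the stated 8/15 and the expected size of 24.

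**2. Success cut-off (assumed).** The plan enrolls 24 and states no cut-off. Under p=0.50, P(X>=16 of 24)=0.076 and P(X>=17 of 24)=0.032. I use 17 or more, the smallest count with an exact one-sided p below 0.05.

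**3. Share replaced (assumed).** Let s be the share of treated patients with SD who come off after Induction. The documents give no value; I show 5%, 10% and 20%.

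**4. Apparent ORR if replaced patients are not counted.** With response as CR/PR and a true rate of 0.50, the counted rate is p = 0.50/(1-s):
- s=5%: 0.50/0.95 = 0.526
- s=10%: 0.50/0.90 = 0.556
- s=20%: 0.50/0.80 = 0.625

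**5. Type I error on the same condition.** There are two ways to apply it.
- (a) All first 15 enrolled stay in stage 1, as 10.1.2 literally says, and replaced patients drop out only of the final 24. With x responders and d replaced patients among the first 15, 9+d further counted patients are needed. Sum over x>=9 and over d: Mult(x, d; 15; 0.50, s) × P[Bin(9+d, p) >= 17-x].
- (b) Replaced patients drop out of both counts. Sum over x>=9: P[Bin(15, p)=x] × P[Bin(9, p) >= 17-x].

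| s | Apparent ORR | Type I error (a) | Type I error (b) | Enrolled to reach 24 not replaced, 24/(1-s) |
|---|---|---|---|---|
| 0 | 0.500 | 0.032 | 0.032 | 24 |
| 5% | 0.526 | 0.051 | 0.055 | 25.3 |
| 10% | 0.556 | 0.080 | 0.094 | 26.7 |
| 20% | 0.625 | 0.164 | 0.265 | 30.0 |

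Under (b) the futility stop also weakens. The chance of passing stage 1 under the null rises from 0.304 to 0.470 at s=10%.

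**6. Sensitivity to the cut-off, version (b).** With success at 18 or more of 24, type I error is 0.011 at s=0, 0.041 at 10% and 0.145 at 20%. With the full 8/15, 26/43 design it is 0.050 at s=0, 0.095 at 5%, 0.172 at 10% and 0.470 at 20%.

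**7. If 6.2.1.1 governs the count.** An SD patient with three brentuximab doses and a scan is classified and stays in the denominator, so steps 4 and 5 do not apply. 4.9 still brings in a substitute, so enrollment runs past 24 by an amount that depends on outcomes (last column), and nothing says how 24 is then to be read.

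**The case against.** **Replacement is not exclusion.** This is the strongest reply, and it stands. A reader might infer that the plan removes SD patients from the ORR, and so that its type I error is inflated as written. The documents do not support that. 4.9 only calls for another patient, and the one explicit rule on who is evaluable, 6.2.1.1, keeps a scanned SD patient who has had three doses. Both sections can be obeyed together. What they leave open is whether the 15 and the 24 include the replaced patient, the substitute or both.

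**Withdrawn may not cover SD.** 4.1.3 speaks of coming off treatment, and 4.8 ties investigator withdrawal to safety, behavioral or administrative reasons. Against this, 4.7 divides patients who are off treatment into those who completed it and those withdrawn for any reason, and the list in 4.8 includes a physician's judgment that continuing is not in the patient's best interest. Replacement is the natural literal reading, but not the only possible one.

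**Direction.** 2.3.2 lists SD as response. On that wording, leaving SD patients out would lower the rate: at a true 0.50 and s=10%, (0.50-0.10)/0.90 = 0.444. CR/PR is the better-supported meaning (7.5, 9.2.2), but the upward bias depends on it. On the 2.3.2 wording, 4.9 would replace patients who had met the endpoint, which is no better.

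**Size.** Neither s nor the cut-off is in the documents. At s=5% with the first 15 kept whole, 0.051 is practically nominal, and a cut-off of 18 keeps type I error below 0.05 at s=10%. The figures are therefore illustrations.

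**Conclusion.** The point holds as a defect in the replacement rule. On its literal wording, 4.9 mandates replacement on the default SD path in 4.1.3, spares PD and spares SD patients given discretionary Consolidation. Neither 4.9 nor Section 10 says who then counts toward the 15 and the 24.

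An inflated ORR is a conditional consequence. It requires that replaced SD patients are not counted, despite 6.2.1.1, and that response means CR or PR. On those conditions, with success at 17 or more of 24 and the 8/15 stop, type I error rises from 0.032 to about 0.05, 0.08-0.09 and 0.16-0.27 for assumed SD shares of 5%, 10% and 20%. If 6.2.1.1 governs there is no such bias, only enrollment beyond 24 that depends on outcomes. The change should be made because the rule is mandatory and outcome-dependent in a single-arm test against a fixed rate, and because the choice would otherwise be made with results in hand.

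**What to change.** - **4.9:** State that a treated Phase II patient is not replaced if a post-Induction response assessment has been done, or if the patient stops for inadequate response or starts other anti-lymphoma therapy at any time. Keep replacement only for untreated patients and for those who leave before the first re-staging scan for reasons unrelated to disease, response or toxicity.
- **6.2.1.1 and 10.1.2:** State that non-replaced patients with measurable disease who have no documented CR or PR before coming off, or before other therapy, are non-responders and count in both the 15 and the 24. A patient switched to chemotherapy before the scan is then counted and not replaced.

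The cost is a few sentences, with no extra scans. Enrollment is no longer pushed toward the 25 to 30 that replacing SD patients implies for s of 5% to 20%. The downside is a possibly lower reported ORR if SD patients do come off after Induction.
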